11. PHARMACEUTICAL INFORMATION

A list of the adverse events and potential risks associated with Daratumumab can be found in Section 9.2.1.

11.1 Daratumumab

11.1.1 Physical Description of Study Drug

Daratumumab is supplied as a colorless to pale yellow preservative-free solution for intravenous infusion in single-dose vials. Daratumumab drug product is formulated as a concentrate of 20 mg/mL \pm 2 mg/mL in an isotonic buffer consisting of sodium acetate, sodium chloride, mannitol and polysorbate 20 at pH 5.5. It will be manufactured and provided under the responsibility of Janssen. Study drug labels will contain information to meet the applicable regulatory requirements.

11.1.2 Storage and Stability

All study drug vials must be stored in the original carton in a refrigerator ranging from 2°C to 8°C and must not be utilized after the expiry date printed on the label. The product must be protected from light and must not be frozen. Daratumumab does not contain preservatives; therefore any unused portion remaining in the vial must be discarded.

11.1.3 Handling

Qualified personnel, familiar with procedures that minimize undue exposure to themselves and the environment, should undertake the preparation, handling, and safe disposal of the chemotherapeutic agent in a self-contained and protective environment.

11.1.4 Availability and Ordering

Daratumumab will be provided free of charge by Janssen Scientific Affairs, LLC as 400mg/20ml vials. Biologics, Inc. will provide drug distribution services for the study. In the event that 400mg/20mL vials are not available, Janssen Scientific Affairs, LLC will provide an equivalent formulation of daratumumab in 100mg vials as a substitute.

The Janssen Scientific Affairs internal study number is [REDACTED].

CONFIDENTIAL

This document is confidential. Do not disclose or use except as authorized.

Biologics, Inc. contact details for drug ordering:

[REDACTED]

Throughout the course of the study, a Biologics, Inc. clinical hotline support, staffed with clinical pharmacists, is made available 24/7/365 in the event an investigator or site coordinator has a question.
Hotline phone#: [REDACTED]

11.1.5 Preparation

Daratumumab will be diluted in a sterile, pyrogen-free physiological saline solution (0.9% NaCl) prior to IV administration in accordance with the site's standard operating procedures (SOPs) for commercial daratumumab.

11.1.6 Administration

Administer the diluted solution by intravenous infusion using an infusion set fitted with a flow regulator and with an in-line, sterile, non-pyrogenic, low protein-binding polyethersulfone (PES) filter (pore size 0.22 or 0.2 micrometer). Polyurethane (PU), polybutadiene (PBD), PVC, PP or PE administration sets must be used. Do not infuse daratumumab concomitantly in the same intravenous line with other agents. Infusion rate of daratumumab and infusion procedures should be in accordance with the site's SOPs for commercial daratumumab. The infusion of daratumumab should not exceed 15 hours.

For sites utilizing the rapid daratumumab infusion (Barr et al.) rate as part of their local institutional standards, please refer to [Appendix F](#) for guidance on preparation and administration.

11.1.7 Accountability

The investigator, or a responsible party designated by the investigator, should maintain a careful record of the inventory and disposition of the agent using the NCI Drug Accountability Record Form (DARF) or another comparable drug accountability form. (See the NCI Investigator's Handbook for Procedures for Drug Accountability and Storage.)

11.1.8 Destruction and Return

The Drug Accountability Log will contain the date and amount of study drugs received, and unused vials destroyed. All used and partially used study drug will be destroyed by the site, in accordance with the site's SOPs. All expired vials of study drug will be destroyed by the site, in accordance with the site's SOPs.

12. BIOMARKER, CORRELATIVE, MRD ASSESSMENT, AND SPECIAL STUDIES

This trial will provide samples of high-risk MGUS and low-risk SMM patients treated with daratumumab to

CONFIDENTIAL

This document is confidential. Do not disclose or use except as authorized.

comprehensively characterize the MM genome and immune cells function and define molecular events driving development and progression of MM.

We will attempt to obtain samples on all patients at the following time points: before therapy, day 1 of each cycle, end of treatment, every three months during follow up, at the time of response determination (CR) and at disease relapse, and at the time of completion of the study. It is anticipated that approximately 90% of samples collected will be adequate for sequencing studies proposed. Samples will be kept until exhausted.

The tumor cells will be collected as described below. From these samples, high quality DNA (for tumor cells) and RNA (for tumor cells and immune cells) for both exome sequencing and RNA sequencing will be obtained. Germline DNA will be also obtained from a buccal swab from all patients at any time point of the study.

Peripheral blood and bone marrow derived mononuclear cells will undergo immunologic assessments to assess the impact of therapy on general measures of cellular immunity, MM reactive T cells, and antigen specific immunity. The percentage of circulating and bone marrow derived regulatory immune cells will be determined.

12.1 Minimal residual disease assessment (MRD)

Bone marrow samples will be collected per the collection time described in the table of sample collection (appendix b). Samples for MRD testing will be collected on all patients who achieve a VGPR or better in treatment or during follow-up at the specified timepoints laid out in Appendix B.

MRD will be assessed using Adaptive's LymphoSIGHT platform as part of normal clinical care for Dana-Farber Cancer Institute patients only in patients that experience a Very Good Partial Response or better. Bone marrow samples will be collected per the collection time described in the sample collection table. The samples will be prepared in the [name] lab and sent for testing in bulk by Adaptive at an undetermined time during the study for analysis.

Using Adaptive's LymphoSIGHT platform, rearranged immunoreceptor loci from genomic DNA will be extracted, amplified, and sequenced using V and J segment primers for each immunoreceptor gene. Tumor-specific clonotypes will be identified for each patient based on their high prevalence in bone marrow. Sequences will be analyzed using standardized algorithms for clonotype determination. Adaptive MRD levels will be quantified using spiked-in reference sequences. Adaptive Inc. will hold samples for up to 6 months after they have been analyzed, and then will subsequently destroy the samples after exhaustion of the DNA.

12.2 Correlative Studies

Correlative studies will be performed to determine:

1. Clonal evolution during therapy and at time of progression (using whole exome sequencing)
2. Immune cell activity and numbers before therapy and during therapy

CONFIDENTIAL

This document is confidential. Do not disclose or use except as authorized.

12.2.1 Exome sequencing of tumor cells

Whole-exome capture libraries will be constructed from 100ng of tumor and normal DNA followed by shearing, end repair, phosphorylation and ligation to barcoded sequencing adapters. The DNA will be size-selected to exonic hybrid capture using SureSelect v2 Exome bait (Agilent, CA). Samples will be multiplexed and sequenced on Illumina HiSeq flowcells with the goal of an average depth of coverage of 100x. The resulting data will be analyzed with the current Illumina pipeline, which generates data files (BAM files). The details of the current analysis pipeline are published elsewhere^{10,56}. Briefly, somatic single nucleotide variants are determined using the MuTect algorithm⁵⁷. Indels and translocations are determined by the algorithms IndelLocator and dRanger, respectively. The MutSig algorithm identifies genes in which the observed mutations are inconsistent with what would be expected at random⁵⁸. To accurately assess the significance of mutations, MutSig takes into account several covariates, which influence the background mutation model. These include the expression level of genes (for which published gene expression data of MM samples can be used), and other gene characteristics observed empirically to co-vary with mutation rate: local relative replication time⁵⁹, and open vs. closed chromatin status⁶⁰. Focal as well as arm-level copy number variations will be determined based on whole exome sequencing and subsequent application of the GISTIC algorithm⁶¹.

The DNA library will be prepared at the [name] Lab, and then sequencing will be done at the following external lab:

Broad Institute Genomics Services

[REDACTED]
[REDACTED]

Sequencing data will then be provided back to [name] lab in the form of BAM file. The samples that are sent for analysis are exhausted during the process, and thus not able to be returned.

12.2.2 RNA sequencing of tumor cells

For RNA Sequencing, poly-A selection and cDNA synthesis will be performed, followed by library preparation, sequencing (76bp or 101bp paired reads), and sample identification with quality control. Details of experimental design are described in^{62,63-65}. We will perform library construction using a non-strand specific Illumina TruSeq Protocol and sequence coverage to 100M total reads. Analysis will be performed as described in the preliminary data and in previous studies⁶³⁻⁶⁵.

The DNA library will be prepared at the [name] Lab, and then sequencing will be done at the following external lab:

Broad Institute Genomics Services

[REDACTED]
[REDACTED]

CONFIDENTIAL

This document is confidential. Do not disclose or use except as authorized.

Sequencing data will then be provided back to [name] lab in the form of BAM file. The samples that are sent for analysis are exhausted during the process, and thus not able to be returned.

12.2.3 Immune cell characterization in peripheral blood and bone marrow

Peripheral blood and bone marrow derived mononuclear cells will undergo immunologic assessments to assess the impact of therapy on general measures of cellular immunity. We will determine the number of immune cells (T-regs, CD4 effector T cells, CD8 T-regs, CD8 effector T cells, NK, NKT, B cells, MSCs, M1 and M2 macrophages, Dendritic cells and MDSCs) at screening and during therapy. These cells will be quantified using CyTOF at DFCI. Each cell type will be defined by unique combinations of antibodies based on previous publications^{66,67}. Regulatory T cells will be defined as CD4/CD25/FOXP3+ cells. Levels of naïve, effector and central memory cells will be quantified as CD45RA, CD45RO/CD62L-/CD27- and CD45RO/CD62L+/CD27+ cells, respectively. NK cells will be quantified by expression of CD56+ subsets. MDSCs will be quantified by CD33+/lineage-/DR- and CD11b/lineage-/DR- cells. CD38 expression in these immune cell subpopulations will be examined, and the CD38+ groups will be evaluated for response to daratumumab. We will also examine the percent expression of checkpoint regulators and how they are modulated with therapy. These checkpoint regulators include PD-1, Lag-3, Tim-3 and CTLA-4.

12.2.4 T cell specific responses

Previous daratumumab clinical studies in myeloma have demonstrated robust T cell changes in the daratumumab treated patients, with significant CD8+ T cell expansion that was higher in responding patients compared to non-responders. In addition, naïve CD8+ T cells decreased, and central memory CD8+ T cells increased. T cell clonality was monitored by TCR sequencing (Immunoseq™) and significantly increased with daratumumab treatment. Responders had significantly higher changes in clonality compared to non-responders. In addition, CD38+ immune suppressive cells (regulatory T cells, MDSC) were noted to decrease with daratumumab treatment. This data suggests that daratumumab may increase the adaptive immune response against malignant disease, and in patients with pre-malignancy who are treatment naïve, this immune response could be even more robust. Therefore, we will examine the T cell response to daratumumab treatment in this study through in depth immunophenotyping (flow or CyTOF), functional studies examining T cell response pre- and post-daratumumab treatment.

12.2.5 RNA sequencing of immune cells during therapy

We will dissect molecular alterations that occur in these cells during progression in MM and the role of therapy on these cells. We will obtain the T-regs, NK cells and MDSCs from the peripheral blood and bone marrow at the same time points described above. Similar samples will be obtained from the comparative untreated cohort. The cells will be isolated by flow sorting and submitted for RNA sequencing as described above.

The RNA library will be prepared at the [name] Lab, and then sequencing will be done at the following external lab:

Broad Institute Genomics Services

CONFIDENTIAL

This document is confidential. Do not disclose or use except as authorized.

Sequencing data will then be provided back to [name] lab in the form of BAM file. The samples that are sent for analysis are exhausted during the process, and thus not able to be returned.

12.3 Bone Marrow Aspirate Samples

Collection of bone marrow aspirate specimens for exploratory analysis is voluntary for this study and will be obtained at the times of bone marrow collections. Specimens will be shipped (via traceable carrier) to and subsequently processed, analyzed, and stored at Dana-Farber Cancer Institute.

12.3.1 Specimens Required

- 2 Purple Top Tubes (EDTA), 10mL each. At certain timepoints, an additional 3ml Purple Top Tube (EDTA) is requested. Specimens should be collected on Mondays to Thursdays for same-day shipment.

12.3.2 Processing Information

- Package tubes at room temperature and wrap in a liberal amount of paper towel around the tubes to ensure adequate insulation of the specimen(s) and absorption in the event of a breakage. Place wrapped specimen in a biohazard labeled Ziploc bag with a fridge pack and zip close. Wrap bubble wrap around the bag and place in a cardboard box. If space remains in the box, stuff with extra paper towel to reduce shifting of samples. Complete the shipping requisition form using the address listed below. Prepare the package for shipping, applying packing tape as needed. Ship the package using FedEx or UPS next day or overnight delivery the same day the sample was collected. Please only ship Monday-Thursday.

12.3.3 Shipping Information

- Label all specimens with the following: Subject Initials, Subject study number (will include protocol number), Visit at which sample was drawn (screening, response or relapse/progression), Date sample drawn (mm/dd/yyyy), Time sample drawn (24 hour clock)

12.3.4 Shipping Instructions:

Shipments must be sent on the day of collection and cannot be batched.

1. An inventory sheet including a complete list of samples shipped (patient number, timepoint, study #) must accompany each shipment. Please sign and date the form.
2. An electronic copy (Word or Excel) of the sample list must also be sent via email. The listing must also include a contact name, address and phone number of the person who is responsible for the shipment.
3. Please email the Lead Site Research Project Manager to notify of an incoming shipment.

CONFIDENTIAL

This document is confidential. Do not disclose or use except as authorized.

4. Please ship Monday to Thursday as shipments cannot be received on weekends and/or on holidays.
5. Once drawn, samples may be shipped **via overnight air** to:

Dana-Farber Cancer Institute
[name] Lab

Email: [REDACTED] Please retain a copy for site record maintenance.

Please see Appendix B and Appendix C for Collection Schedule and Requisition Form.

12.4 Peripheral Blood Samples

Collection of peripheral blood specimens (including serum and plasma) for exploratory analysis is voluntary for this trial. Please see Appendix B for a list of timepoints and specific instructions. These collections will be taken at the time of routine blood collection timepoints required for this study. Specimens will be processed on site according to instructions below and shipped (via traceable carrier) to Dana-Farber Cancer Institute. Once the shipment is received, samples will be subsequently processed, analyzed, and stored at Dana-Farber.

12.4.1 Specimens Required

- 2-3 x 10 mL Purple Top Tubes (K2EDTA) and 1 x 6mL Red Top Tube must be collected Mondays to Thursdays for same-day shipment.

12.4.2 Shipping Information

- Label all specimens with the following:
 - Subject Initials, Subject study number (will include protocol number), Visit at which sample was drawn (screening, response or relapse/progression), Date sample drawn (mm/dd/yyyy), Time sample drawn (24 hour clock)

12.4.3 Shipping Instructions:

- Shipments must be sent on the day of collection and cannot be batched.

12.4.4 Processing Information:

Once collected, the vacutainers will be refrigerated and stored according to instructions below. There is no required processing for purple or red top tubes at each participating site prior to shipment.

Package tubes at room temperature and wrap in a liberal amount of paper towel around the tubes to ensure adequate insulation of the specimen(s) and absorption in the event of a breakage. Place wrapped specimen in a biohazard labeled Ziploc bag with a fridge pack and zip close. Wrap bubble wrap around the bag and place in a cardboard box. If space remains in the box, stuff with extra paper towel to reduce shifting of samples. Complete

CONFIDENTIAL

This document is confidential. Do not disclose or use except as authorized.

the shipping requisition form using the address listed below. Prepare the package for shipping, applying packing tape as needed. Ship the package using FedEx or UPS next day or overnight delivery the same day the sample was collected. Please only ship Monday-Thursday.

With each shipment, please include the following:

1. An inventory sheet including a complete list of samples shipped (patient number, timepoint, study #) must accompany each shipment. Please sign and date the form, and retain a copy for site record maintenance. **See Appendix C for Sample Requisition Form.**
2. An electronic copy (Word or Excel) of the sample requisition form must also be sent via email and include the tracking number of the package. The listing must also include a contact name, address and phone number of the person who is responsible for the shipment.
3. Please email the Lead Site Research Project Manager to notify of an incoming shipment.
4. Please ship Monday to Thursday as shipments cannot be received on weekends and/or on holidays.
5. Once drawn, samples may be shipped **via overnight air to:**

Dana-Farber Cancer Institute
[name] Lab

Please retain a copy for site record maintenance.

13. MEASUREMENT OF EFFECT

13.1 Development of symptomatic disease

In this study, patients may continue on study until the development of symptomatic MM that requires therapy. This is defined as one of the following criteria (CRAB and Myeloma defining events < MDE):

- Increased calcium levels (corrected serum calcium >0.25 mmol/dL above the upper limit of normal or >0.275 mmol/dL) due to myeloma
- Renal insufficiency (attributable to myeloma);
- Anemia (Hb 2g/dL below the lower limit of normal or <10 g/dL) due to myeloma
- Bone lesions (lytic lesions or generalized osteoporosis with compression fractures)
- Or any MYELOMA DEFINING EVENTS (MDE) as follows:
 - Clonal bone marrow plasma cell percentage $\geq 60\%$ ²⁰
 - An abnormal FLC-ratio ≥ 100 (involved kappa) or <0.01 (involved lambda)²¹
 - >1 focal lesions (≥ 5 mm) on MRI or PET-CT studies^{22,23}

CONFIDENTIAL

This document is confidential. Do not disclose or use except as authorized.

For measurement of response:

The disease response will be assessed using criteria based on the International Working Group Uniform Response Criteria in Section 14.2.2.1. If the only measurable parameter is serum immunoglobulins free light chain (FLC), the participant will be followed by IMWG Response Criteria provided in Section 13.2.2.2

Disease response by the Modified EBMT Response Criteria in Section 13.2.2.3 will also be collected on participants as a secondary measure.

The same method of assessment and technique should be used for disease measurement at baseline and during follow-up. Disease response should be confirmed by two consecutive assessments.

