For SMM patients a M-protein \geq 3 g/dL, a FLC ratio outside the range of 0.125 to 8, and \geq 10% plasma cells in the bone marrow are considered as adverse factors in this model^{24,25}. The 5-year rate of progression in patients with 1, 2 and 3 risk factors was 25%, 51% and 76% respectively. The time to progression with these risk factors was 10, 5.1 and 1.9 years respectively. Recently Rajkumar et al have proposed that SMM with >60% plasma cells progress to multiple myeloma within 2 years in 95% cases and should be treated at diagnosis even in the absence of symptoms²⁰.

Table 1: Definitions currently available for MGUS and smoldering myeloma

International Myeloma Working Group criteria, 2010 version³²	
MGUS	
 ▪ Serum M protein <3 g/dL ▪ Clonal bone marrow plasma cells <10% ▪ Absence of myeloma defining events and amyloidosis
SMM	
 ▪ Serum M protein \geq3 g/dL ▪ and/or clonal bone marrow plasma cells 10% - 60% ▪ or urinary monoclonal protein \geq500 mg per 24 hours ▪ or FLC ratio < 0.125 or > 8 ▪ or \geq 95% abnormal plasma cells in the bone marrow ▪ or immunoparesis of one or more immunoglobulins ▪ Absence of myeloma defining events and amyloidosis
MM	
 ▪ Clonal bone marrow plasma cells \geq10% and/or biopsy proven plasmacytoma ▪ Presence of serum and/or urinary monoclonal protein at any level ▪ Evidence of end organ damage that can be attributed to the underlying plasma cell proliferative disorder (CRAB criteria) 
 ○ Hypercalcemia: Serum calcium >0.25 mmol/L above upper limit of normal or > 2.75 mmol/L (> 1 mg/dL above upper limit of normal) ○ Renal insufficiency: Serum creatinine > 173 μmol/L (>2 mg/dL) ○ Anemia: Normochromic, normocytic with a hemoglobin value of >2 g/dL below the lower limit of normal or a hemoglobin value <10 g/dL ○ Bone lesions: Lytic lesions, or osteoporosis with compression fractures ▪ Or any MYELOMA DEFINING EVENTS (MDE) as follows: 
 ○ Clonal bone marrow plasma cell percentage* > 60%²⁰ ○ An abnormal FLC-ratio \geq100 (involved kappa) or <0.01 (involved lambda)²¹>1 or more focal lesions on MRI or PET-CT studies(\geq^{22, 23}

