2.5 Definition of SMM and MM

The diagnosis of smoldering (asymptomatic) multiple myeloma (SMM) is based on^{48,49}:

- Serum monoclonal protein (IgG or IgA) ≥ 3 g/dL or urinary monoclonal protein ≥ 500 mg per 24 h and/or clonal bone marrow plasma cells (BPMC) 10–60%.
- Absence of myeloma defining events or amyloidosis
- No evidence of the following CRAB criteria* or other Myeloma defining events (MDE):
 - Increased calcium levels (corrected serum **calcium** >0.25 mmol/dL above the upper limit of normal or $>.275$ mmol/dL) related to MM
 - **Renal** insufficiency (attributable to MM)
 - **Anemia** (Hb 2g/dL below the lower limit of normal or <10 g/dL) related to MM
 - **Bone** lesions (lytic lesions or generalized osteoporosis with compression fractures)

New MDE criteria that indicates overt MM and not SMM^{48,49}

The following criteria are now incorporated with the CRAB criteria to indicate that patients meet criteria for therapy as symptomatic or overt MM:

- Bone marrow plasma cells $>60\%$
- Serum involved/uninvolved FLC ratio ≥ 100 , provided the absolute level of the involved free light chain is at least 100 mg/L and repeated twice (except for monoclonal light chain smoldering MM and for those with stable serum light chains for 6 months.)
- MRI with >1 focal lesion that is at least 5 mm or greater in size

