3. PARTICIPANT SELECTION

3.1 Eligibility Criteria

3.1.1 Age \geq 18 years

3.1.2 Must meet criteria for high-risk MGUS or low-risk smoldering myeloma as described below:

High-Risk MGUS

Must have <10% plasma cells and <3.0g/dL M-spike and at least 2 of the following 3 criteria:

1. Abnormal free light-chain (FLC) ratio (<0.26 or >1.65)
2. M-protein concentration (≥ 1.5 g/dL)
3. Non-IgG M protein (including IgA)

Low-Risk Smoldering Multiple Myeloma

Must only present with 1 of the following criterion:

CONFIDENTIAL

This document is confidential. Do not disclose or use except as authorized.

1. Monoclonal Protein ≥ 3 g/dL
2. $\geq 10\%$ Bone Marrow Plasma Cells
3. FLC ratio < 0.125 or > 8

3.1.3 No evidence of CRAB criteria[†] or new criteria of active MM which including the following:

- Increased calcium levels (corrected serum calcium >0.25 mmol/dL above the upper limit of normal or >0.275 mmol/dL)
- Renal insufficiency (attributable to myeloma)
- Anemia (Hb 2 g/dL below the lower limit of normal or <10 g/dL)
- Bone lesions (lytic lesions or generalized osteoporosis with compression fractures)
- No evidence of the following new criteria for active MM including the following: Bone marrow plasma cells $>60\%$, Serum involved/uninvolved FLC ratio ≥ 100 , and MRI with more than one focal lesion

[†] Participants with CRAB criteria that are attributable to conditions other than the disease under study may be eligible

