8.3 Criteria for Taking a Participant Off Protocol Therapy

Patients will be informed that they have the right to withdraw from the study at any time for any reason, without prejudice to their medical care.

In the absence of treatment delays due to adverse event(s), treatment may continue for 20 cycles or until one of the following criteria applies:

- Progression to overt Multiple Myeloma as described in Section 2.1 Table 1
- Intercurrent illness that prevents further administration of treatment
- Unacceptable adverse event(s)

CONFIDENTIAL

This document is confidential. Do not disclose or use except as authorized.

- Participant decides to withdraw from the protocol therapy
- Participant demonstrates protocol non-compliance that, in the eyes of the investigator, jeopardizes patient safety or the endpoints of the trial.
- General or specific changes in the participant's condition render the participant unacceptable for further treatment in the judgment of the treating investigator

Participants will be removed from the protocol therapy when any of these criteria apply. The reason for removal from protocol therapy, and the date the participant was removed, must be documented in the case report form (CRF). Alternative care options will be discussed with the participant.

The reason for taking a participant off treatment, and the date the participant discontinued study treatment, must be documented in the case report form (CRF) and conveyed immediately to the Lead Site Research Project Manager.

In the event of unusual or life-threatening complications, treating investigators must immediately notify the Overall PI, [name] at telephone # [REDACTED]

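### Section 13.1 and Table 1 count a free light chain ratio of 100 or more as a myeloma event without the level floor and repeat that Section 2.5 requires

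*Combined protocol and SAP*

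**What the plan says.** Section 2.5 lists the newer criteria that mark overt MM. A ratio of at least 100 counts "provided the absolute level of the involved free light chain is at least 100 mg/L and repeated twice", and the text adds "except for monoclonal light chain smoldering MM and for those with stable serum light chains for 6 months".

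Section 13.1 sets the on-study event of symptomatic MM: "This is defined as one of the following criteria". One listed item is "An abnormal FLC-ratio ≥ 100 (involved kappa) or <0.01 (involved lambda". It has no floor, repeat or exception, and does not refer to Section 2.5.

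Section 8.3 ends protocol therapy on "Progression to overt Multiple Myeloma as described in Section 2.1 Table 1". The MM entry in Table 1 opens with marrow plasma cells of at least 10% "and/or biopsy proven plasmacytoma". It then asks for M-protein in serum or urine and for end-organ damage, and finally adds the myeloma-defining events (MDEs) after the word or. Its FLC item is again the ratio alone. Section 3.1.3 excludes patients at screening on the ratio alone.

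Section 8.4 plans to record time until active symptomatic MM and requires a CRAB/MDE assessment in follow-up. Section 15.1 does not make that time an endpoint.

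**The concern.** The protocol holds two definitions of one event. The stricter sits in Background; the looser sits where sites take their instructions. A site that follows 13.1 must record symptomatic MM on a result that Section 2.5 does not accept as overt MM.

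Three things are at stake. The label feeds the time to symptomatic MM in Section 8.4 and the objectives that relate genomic and immune findings to progression to MM. The same result may stop treatment under Section 8.3. And one visit can be recorded as both a deep response and a myeloma event.

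**Working it through.** The plan states no figure on this point, so the check sets the definitions side by side and then works out when they disagree.

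**1. Definitions**

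| Place | Use | Ratio | Involved chain ≥100 mg/L | Repeat | Exceptions |
|---|---|---|---|---|---|
| 2.5 | Overt MM (Background) | ≥100 | Yes | Yes | Two |
| 13.1 | Symptomatic MM on study | ≥100 or <0.01 | No | No | None |
| Table 1, via 8.3 | Stop therapy | ≥100 or <0.01 | No | No | None |
| 3.1.3 | Eligibility | ≥100 | No | No | None |

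**2. Does another clause supply the missing conditions?** The two-assessment rules in 13.1, 13.2.2 and 13.2.2.1 concern disease response and response categories. They do not cover the 13.1 event list and set no mg/L floor. Calendar note 10 allows extra draws when clinically indicated but does not make them part of the event.

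**3. When the floor matters.** Ratio = involved / uninvolved ≥ 100 means uninvolved ≤ involved / 100. With the involved chain below 100 mg/L, the uninvolved chain must be below 1.0 mg/L: 30/100 = 0.3, 60/100 = 0.6, 90/100 = 0.9 mg/L at most. The missing repeat matters at any level.

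**4. Example with assumed values.** High-risk MGUS entry under Section 3.1.2: "Must have <10% plasma cells and <3.0g/dL M-spike and at least 2 of the following 3 criteria".
- Entry: M-protein 2.0 g/dL, marrow <10%, involved 300 and uninvolved 6 mg/L. Ratio 300/6 = 50. The patient qualifies on ratio and M-protein and is below the 3.1.3 limit.
- Later: M-protein 0.15 g/dL, involved 60 and uninvolved 0.5 mg/L.
- M-protein fall: (2.0 − 0.15)/2.0 = 92.5%. Under 13.2.2.1 this is VGPR if urine M-protein is below 100 mg per 24 h and the result is confirmed. FLC plays no part in VGPR for a patient measured by M-protein.
- Ratio: 60/0.5 = 120. Section 13.1 gives symptomatic MM.
- Involved chain: 60 mg/L, below 100, a fall of (300 − 60)/300 = 80%. Section 2.5 does not give overt MM.

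**5. Reach of the stop-therapy rule.** Table 1 can be read two ways. If an MDE stands alone, the ratio by itself triggers 8.3. If an MDE only replaces the end-organ-damage item, 8.3 also needs marrow of at least 10% or a plasmacytoma, with M-protein present, at that time. Under this second reading:
- A patient who enters with at least 10% marrow may have only that one SMM criterion, so the entry ratio lies between 0.125 and 8. It must move at least 100/8 = 12.5-fold (or 0.125/0.01 = 12.5-fold) to reach the trigger.
- A patient who enters with a ratio above 8 or below 0.125 has marrow below 10%. Without a plasmacytoma, 8.3 does not apply unless marrow later reaches 10%. The example patient is in this group.

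**6. Opportunities and scale.** FLC is scheduled on Day 1 of 20 cycles, at end of treatment, and every 6 or 3 months for up to 5 years: 20 + 1 + 10 = 31 to 20 + 1 + 20 = 41 tests for a patient who completes the schedule. For scale only, suppose all 50 patients were untreated low-risk SMM at the 25% five-year risk quoted in the Introduction (Section 1). Then 50 × 0.25 = 12.5 events are expected, and one false event would equal 1/12.5 = 8% of them. The trial also enrols MGUS and treats everyone, so the true number could well be smaller.

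**The case against.** The strongest reply is that the operative rules agree. Sections 3.1.3, 13.1 and Table 1 all use the ratio alone, and no operative clause cites Section 2.5, so sites have one FLC instruction and the stricter version is a preference. No Section 15 analysis uses the 13.1 label. Section 13.1 speaks of disease needing therapy and 8.3 of progression, and an investigator would hardly apply either to a patient whose M-protein fell 92.5%. Marrow and imaging are expected at suspected progression. The frequency is unknown, and the layout of Table 1 is damaged in the text available.

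Much of this stands:
- A reader might infer that 3.1.3 wrongly excludes patients. The documents do not support that: barring any ratio of at least 100 is a defensible, cautious entry rule in a low-risk population.
- A reader might infer that any such ratio ends therapy. It does so only under the conditions in step 5 of the working, and for the example patient the matter is open.
- Section 2.5 does not settle how many repeat samples it wants. One confirmatory sample is a choice for the sponsor.

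The rest does not remove the conflict. Section 2.5 presents its list as the criteria for treating a patient as having overt MM, not as illustration. Section 13.1 defines symptomatic MM by its list, so the reference to needing therapy adds no further test. An investigator who declines to record the event is departing from 13.1, and event dates would then depend on who judged. Nor does work-up at suspected progression make the floor or the repeat part of the event.

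**Conclusion.** The point holds and should be corrected. Sections 13.1 and 2.5 disagree on whether an unrepeated ratio, or one with a low involved chain, is myeloma, and the looser text governs the on-study label. The effect on stopping therapy is conditional on the reading of Table 1, or on marrow (or plasmacytoma) and M-protein status at the time. The number of patients affected is unknown; the example values are assumptions.

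A reader might infer that the primary result is compromised. The documents do not support that. For patients measured by M-protein, VGPR does not use FLC, and IMWG progression in 13.2.2.1 does not use the FLC ratio. An exact binomial check of the rule of 32 or more of 50 reproduces the plan: type I error 0.032 at 50%, power 86% at 70% and 97% at 75%. The only route to the primary endpoint is indirect, through therapy stopped before a VGPR is reached, and the documents give no rate from which to size it.

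A reader might also infer that the label takes patients off study. Section 8.5 does not list symptomatic MM among its reasons.

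The marrow cut-off also differs: Table 1 writes "Clonal bone marrow plasma cell percentage* > 60" percent, while 13.1 includes exactly 60%. This matters only at that single value and adds no weight.

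**What to change.** Use one FLC-ratio definition in 13.1 and Table 1, cited by 8.3 and 8.4: ratio at least 100 or below 0.01, involved chain at least 100 mg/L, confirmed on a repeat sample, with the event dated at the first qualifying sample. The sponsor should state:

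- how many repeats are required;
- whether the Section 2.5 exceptions waive the whole criterion or only the floor and repeat;
- whether an MDE in Table 1 stands alone.

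On treatment, the next cycle's FLC can serve as the repeat. In follow-up, scheduled tests are 3 or 6 months apart, so ask for a prompt unscheduled draw, for example within about 4 weeks. For patients already treated, reclassify from the FLC values already collected as a sensitivity check, and show separately anyone with no second FLC before new therapy. Aligning 3.1.3 is optional. The 60% cut-off can be harmonised in the same amendment.

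The cost is a protocol clarification, some unscheduled FLC draws and one small analysis, with no new assay. The downside is that stopping in a true FLC-only event may be delayed by up to about one cycle (4 weeks, plus the 7-day visit window), or less with an unscheduled draw. CRAB features and the other MDEs would still be acted on at once.
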